Familial Hypercholesterolemia	
DO NOT include the following:	DO NOT include the following:
Low HDL	Pulmonary hypertension
	Intracranial hypertension
	Venous hypertension
	Pre-eclampsia or Maternal Hypertension
	Portal hypertension
	Ocular hypertension

Randomization: Prior to study start, [name] will develop a 1:1 blocked randomization scheme, stratified by site. This randomization scheme will be carried out using the randomization module in RedCap. Participants will be randomized by RedCap at the time of their baseline visit to avoid randomizing participants who have not yet completed consent.

Education control group: Participants assigned to the education group will receive usual care enhanced with general prevention education delivered by the prevention nurse. This active comparator is appropriate because participants have multiple risk factors for ASCVD, and advisory committees for prior studies have recommended this for similar study populations. The prevention educational modules will be delivered at 4 in-person visits (enrollment, 4, 8, and 12 months), and will consist of evidence-based material on diet, exercise, smoking, sexually transmitted infections, and cancer prevention. As recommended by the design teams, control participants will have access to a wide range of educational materials about healthy living, but will not receive additional counseling from the prevention nurse outside of the 4 in-person visits.

All participants in both intervention and education control arms will complete the following study assessments: 1) in-office BP obtained by a trained research assistant blinded to study group using a standardized protocol¹² (0, 4, 8, 12 months); 2) lipid profile (0, 4, 8, 12 months); 3) perceived ASCVD risk survey⁵⁶ (0, 12 months); 4) provider trust and communication survey (0, 12 months). Study visits will be calculated from the date of the baseline enrollment visit in months. Per protocol, study visits must be completed +/- 14 days from the calculated visit date.

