Frequency of contact: All subjects will complete the same assessments at the same time-points (in-office BPs, lipid profile, perceived ASCVD risk survey, and network analysis survey). The prevention nurse will then contact the intervention subjects at up to 2-week intervals as necessary to carry out the multi-component intervention. Frequency of contact will be determined according to protocol triggers that may be patient or prevention nurse initiated (e.g. home BP values are high, checking for side effects after starting a statin). At a minimum, the prevention nurse will have face-to-face meetings at 0, 4, 8, and 12 months, as well as a mid-period telephone call between in-person visits to “check-in” about home BP values and medication adherence. An initial 2-week follow-up call will ensure proper use of the home BP monitor and to address any other questions. Two example scenarios of relatively lower intensity and higher intensity intervention are shown in **Figure 3** with the education control group as a reference. As demonstrated by the figure, a strict attention control group is not appropriate since the dose of attention will vary according to the needs of the participant.

As with control patients above, study visits must be completed +/- 14 days from the calculated visit date. Visits done between 14 and 28 days after the calculated visit date will be considered a protocol deviation. Visits outside of the +28 day window will not be scheduled and that visit will be considered missing for that patient. The fasting lipid panel blood draw will be done at the time of study visit or within a +/- 10 day window. Study calls will be completed +/- 14 days of the scheduled due date. In the event that the study nurse has made no less than three

Protocol

attempts to schedule a participant's follow-up visit, a letter (Appendix R) will be sent to the participant.

[figure not shown]

Figure 3: Example scenarios of intervention participant contact frequency. (A) Participant with lower intensity requirements; (B) Participant with higher intensity requirement; (C) Control participant. Squares represent in-person visits and lines are telephone contact.

EXTRA-CVD Intervention components:

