Other medication side effects: All medications have potential side effects. Medications used in the nurse-managed protocols will be only be recommended by the nurse and must ultimately be prescribed by the subject's treating provider according to his/her best clinical judgement and approval. Common side effects of anti-hypertensive and lipid-lowering medication include but are not limited to: bradycardia, lightheadedness and orthostatic hypotension, lower extremity edema, kidney injury and electrolyte imbalances (see above), and myalgias. Rhabdomyolysis, glucose intolerance, and hepatic injury are rare complications of statin therapy.

Physical activity. All subjects will be encouraged to increase their physical activity, raising the possibility of musculoskeletal injury or unmasking of ischemic heart disease. Risks from increased physical activity will be minimized by encouraging moderate rather than vigorous activity. Providers will respond to these patient problems per usual medical practice.

Smoking. While not a key component of the intervention, all subjects will be encouraged to quit smoking (if currently using), raising the possibility of withdrawal symptoms from nicotine dependence.

Psychological risks. We do not anticipate any substantial psychological risks to be associated with participation in this study. As part of our assessments, we will ask participants about their demographic characteristics (i.e., race/ethnicity, socioeconomic status). It is possible that some participants may feel uncomfortable answering some of these questions. We will only ask questions that involve data that are important for study outcomes, and we will inform patients that they may refuse to answer any interview or survey questions, but still be involved in the study. It is also possible that participants may be uncomfortable talking with the Prevention Nurse about some topics that are included in patient-based intervention.

Protections against risk

The specific risk of participation are noted above; procedures for protection follow.

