Unexpected and serious adverse event reporting: A detailed monitoring plan will be included as part of the study protocol and submitted to the IRB and reviewed and approved by the funding Institute and Center (IC) before the study begins. Prior to initiation of the study, agreement about the data safety monitoring plan will be confirmed in order to ensure the safety of subjects and the validity and integrity of the data. The prevention nurse or research coordinator at each site will report serious adverse events that are unexpected and study related immediately to a study physician who will convey this information to the study team, IRB, and NIH. All AE's and SAE's will be captured, reports will be completed, and entered into the study database. A safety report will detail all serious and unexpected adverse events or other unanticipated problems that involve risk to study participants or others, and whether these appeared to be related to the study-based interventions or research assessment protocols. If the study team, UH IRB, or NIH has concerns regarding SAEs, the UH IRB will be notified and a copy of the safety summary will be filed with the UH and local site IRBs. Actions taken by the UH or local IRB offices in response to adverse event concerns will be reported to the NIH.

Communications between care team providers and the study prevention nurse (electronic medical record, telephone logs, work emails) will be collected as a key process measure of the intervention. We will only examine telephone logs to and from study phones used exclusively for this research study for the purpose of coordinating care of study participants. Similarly, we will examine emails to and from email addresses created specifically for the study. Only secure, HIPAA compliant hospital email platforms will be used. The purpose of this is to protect against collection of any personal communications that are unrelated to the research study.

Potential Benefits of the Proposed Research to the Subject and Others

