Each of these components have multiple procedures to safeguard the wellbeing of study subjects and to maintain the scientific integrity of the project while achieving the study's specific aims. Key components of the data and safety monitoring plan include weekly meetings of core members of the research team (at minimum, the Principal Investigators, Project Director and Research Assistants) and monthly meetings of the extended research team including [name], [name], [name], [name], [name], [name], [name], [name], site prevention nurses and research coordinators.

Meetings of Core Members of the Research Team:

The PIs will run monthly conference calls with the entire study team which will include core protocol team along with study coordinators, prevention nurses, and other representatives from each of the 3 study sites. The agenda for these meetings will include tracking of subject recruitment, enrollment, and retention; data collection and entry; and documentation and review of any subject concerns or adverse effects. These meetings will help ensure that the project timeline is being met.

Regulatory Issues

Adverse Events Protocols:

An adverse event is defined as any reaction, side effect, diagnosis or untoward event that either a) occurs during the course of the clinical trial and was not present at baseline; or b) was

present at baseline and appears to worsen during the study. All AE's will be reported to one of the study PIs. All subjects will be aware of their rights prior to participation and will be encouraged to report any incidents or adverse effects to the investigators and the Case Western Reserve University Institutional Review Board (IRB). Contact information for the investigators and the IRB will be provided in all the consent materials. During assessments the research staff will inquire about AEs and complete an AE form for each subject. In the event that the participant is experiencing a worsening of symptoms, the Research Assistant will, with participant's permission, inform the clinic director. The study PIs, and research staff will together determine if the AE places the participant at risk if study treatment is continued.

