All adverse events, with the exception of clinically insignificant events and minor common illnesses and injuries (e.g., cold/flu, scrapes, upset stomach, low-grade headaches) will be documented on an AE Log. Should any study subjects express concerns about the study and/or their participation in the study or express distress as a result of their participation, the witnessing research team member will document this in the AE Log. AEs will be reported to the study PIs and the study research staff to determine whether and what actions might be appropriate. Any AEs determined to be serious and/or study-related will require the completion of an AE form to be entered into the project database.

During research staff training, procedures for AE identification, collection and reporting will be reviewed in detail. Study staff will be trained to provide crisis intervention and referral as is standard operating procedure within each clinic for such situations, should they become dangerous or life-threatening (i.e. suicidal ideation or attempts).

AEs will be managed in conjunction with clinic medical staff, with permission from the participant. All subjects will be ongoing patients at a study site clinic and thus subjects can be monitored and have access to medical staff throughout the study period.

Data and Safety Monitoring Board

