According to guidelines established by the NIH for clinical trials, the investigators will establish a Data and Safety Monitoring board (DSMB) composed of independent research scientists not otherwise connected with the study. This committee (which is independent of the study investigators) will be set up to monitor the study results for evidence of adverse or beneficial treatment effects throughout the study period. The Monitoring Committee will remain "blinded" to outcome characteristics of the study for as long as possible. While the committee may have access to information that is deemed necessary to make an appropriate determination, highly sensitive information in relation to the outcome of the study will be requested on a "need to know" basis as it may arise during the course of the committee's deliberations. The committee's concerns will be directed to patient accrual rates, appropriate follow-up, compliance, data acquisition, undue complications, and whether the study as it is currently being conducted will be able to answer the proposed hypotheses. Additional responsibilities will include monitoring the integrity of data collection, reviewing training and compliance with all components of the interventions and monitoring for adverse events. The membership and frequency of meeting are at the discretion of the funding institute but will consist of 3-5 members with appropriate expertise, for example in biostatistics, cardiovascular disease, behavioral interventions, HIV research, and clinical trials. It is expected that this committee will meet once per year in person and once via conference call and will report to the funding institute on scientific and administrative issues. We do not anticipate any real harm to patients, but adverse

events will be monitored. Adverse event forms will be used to report all unanticipated events. The following information will be included in the report: date of event, attribution to intervention, and outcome of adverse events. Death will be reported within 24 hours. Unanticipated adverse events will be reported within 7 days. Reports will be submitted electronically to the CWRU IRB and NIH. A written follow-up will be submitted within 30 calendar days. All adverse events (serious or not, related or unrelated, anticipated or unanticipated) will be reported in the annual report to the CWRU IRB and NIH.

The DSMB members and contact information is shown in the following table (members appointed Jan 2019):

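### The protocol gives conflicting rules on which adverse events get a form and reach the database, and in Aim 2 it does not separate events found at visits common to both arms from those found at intervention-only contacts

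*Combined protocol and SAP*

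**What the plan says.** On capture of adverse events (AEs), four statements in the protocol set the rule:

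- Protections against risk, paragraph on unexpected and serious adverse event reporting: "All AE's and SAE's will be captured, reports will be completed, and entered into the study database".
- Regulatory Issues, Adverse Events Protocols, first paragraph: "During assessments the research staff will inquire about AEs and complete an AE form for each subject".
- Same section, next paragraph: all but trivial events and minor everyday illnesses go on an AE Log, and then "Any AEs determined to be serious and/or study-related will require the completion of an AE form to be entered into the project database".
- Data and Safety Monitoring Board (DSMB): AE forms serve to report events that were not anticipated, yet "All adverse events (serious or not, related or unrelated, anticipated or unanticipated) will be reported in the annual report".

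On contacts, Aim 2 Procedures gives both arms the same assessments at 0, 4, 8 and 12 months. Control participants "will not receive additional counseling from the prevention nurse outside of the 4 in-person visits". For the other arm, the nurse will "contact the intervention subjects at up to 2-week intervals as necessary", with a minimum of the four visits, one call midway between each pair of visits, and a call at 2 weeks. The component on home BP monitoring puts participants with poor control on two-weekly calls. Starting a cholesterol drug triggers a call about adherence and side effects. The BP algorithm brings follow-up chemistry panels for certain drug classes. Intervention participants measure BP at home every day, while controls receive a monitor only after the month 12 visit.

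Statistical Considerations contains no analysis of AEs by arm. The DSMB is nevertheless asked to watch for adverse as well as beneficial treatment effects.

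**The concern.** There are two separate problems.

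First, the content of the safety database depends on which paragraph a site follows. The drug effects listed under Potential risks include lightheadedness, edema and myalgia, which are commonly non-serious. Under the rule in the second paragraph of Adverse Events Protocols, required entry of such an event then turns on whether it is called study-related. AEs go to the principal investigators and research staff, and nothing says that those judging relatedness are unaware of the arm. If sites read the rules differently, or judge relatedness with knowledge of the arm, the recorded data may differ by site or arm for reasons other than what happened to participants.

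Second, in Aim 2 the intervention creates extra occasions on which an event can come to light. The protocol expects this itself: its paragraph on BP safety says closer monitoring is likely to reveal more abnormal readings. Without a record of how each event was found, an excess in the intervention arm cannot be divided into true effect and added detection.

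**Working it through.** **Capture rules side by side.** The protocol states no AE rate or count, so there is no figure to reproduce. Two kinds of event show the conflict.

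| Statement | Non-serious, judged unrelated, not trivial | Clinically trivial |
|---|---|---|
| Unexpected and serious adverse event reporting | Database | Database |
| Adverse Events Protocols, first paragraph | Form, if found at an assessment | Form, if found at an assessment |
| Adverse Events Protocols, second paragraph | Log; form and entry not required | Not on the log |
| DSMB | Form if unanticipated; annual report in any case | Form if unanticipated; annual report in any case |

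The rows cannot all be followed as written. The annual report is to contain all events, but under the third row some need not reach the database and others need not reach the log.

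**Scheduled contacts in Aim 2** (Education control group; Frequency of contact):

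- Control: 4 visits, of which 3 follow baseline.
- Intervention minimum: 4 visits + 3 mid-period calls + 1 two-week call = 8, of which 7 follow baseline.
- Intervention at two-weekly contact: 52 / 2 = 26 after baseline.

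Counting baseline in the minimum, 8 / 4 = 2.0. At the upper end, 26 / 4 = 6.5 (27 / 4 = 6.75 if baseline is added to the 26). After baseline, when events can occur, the ratios are 7 / 3 = 2.3 and 26 / 3 = 8.7. For inquiry at the common assessments alone, 3 / 3 = 1.0.

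**What this could do to observed rates.** Contact ratios are not rate ratios. As an illustration, assume the same true event rate in both arms, spread evenly over 52 weeks, with an event recorded only if a contact falls within w weeks after it. Then

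captured share = (weeks lying within w weeks before some contact) / 52.

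Control contacts fall at weeks 17.3, 34.7 and 52. The intervention minimum adds weeks 2, 8.7, 26 and 43.3. The maximum is every second week.

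| Recall window w | Control | Intervention minimum | Intervention maximum | Ratio, minimum | Ratio, maximum |
|---|---|---|---|---|---|
| 2 weeks | 6/52 = 0.115 | 14/52 = 0.269 | 1.000 | 2.33 | 8.67 |
| 4 weeks | 12/52 = 0.231 | 26/52 = 0.500 | 1.000 | 2.17 | 4.33 |
| 8 weeks | 24/52 = 0.462 | 48.67/52 = 0.936 | 1.000 | 2.03 | 2.17 |
| 12 weeks | 36/52 = 0.692 | 1.000 | 1.000 | 1.44 | 1.44 |
| About 17.3 weeks (whole visit interval) | 1.000 | 1.000 | 1.000 | 1.00 | 1.00 |

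The window w is an assumption, because the protocol gives no information on recall. The model also treats every contact as an occasion to ask about events, which overstates the calls made for monitor use, BP values or adherence.

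**The case against.** The strongest reply is that systematic inquiry is already planned on a common schedule: "During assessments the research staff will inquire about AEs and complete an AE form for each subject", and assessments are identical in both arms. Control participants may report events at any time and have access to clinic staff throughout. No by-arm AE comparison is planned, so no stated claim is invalidated. Much of this stands. It means the imbalance affects only events that surface outside the common assessments.

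A reader might infer four stronger things that the documents do not support.

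- That only serious or related events may enter the database. The sentence sets a requirement for those events and keeps a log for others. It does not bar them, and the other statements point to wider capture. The defect is unreconciled wording.
- That AE rates by arm are not comparable, or inflated in proportion to contacts. With full recall at the next visit the ratio is 1.0, and two-weekly contact is a ceiling for most participants.
- That drug effects will be called unrelated because each drug "must ultimately be prescribed by the subject's treating provider". No attribution rule says so, and DSMB reports must record attribution to the intervention.
- That serious events are screened out because site staff "will report serious adverse events that are unexpected and study related immediately to a study physician". That sentence governs immediate escalation. All AEs go to a principal investigator, and serious ones promptly to the IRB and the funder.

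The absence of a planned AE analysis does not remove the point. The DSMB will review safety data by some rule, and none is given.

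**Conclusion.** The contradiction is in current text and holds without any assumption. Under one of the four statements, a non-serious event judged unrelated need not reach the database, and the judgment is not stated to be blinded. Whether any events have been lost this way cannot be told from the documents.

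The detection point holds in a limited form and for Aim 2 only, since the Aim 4 virtual arm has no randomized control. Intervention participants have at least 8 contacts against 4, up to about one every 2 weeks. Some are made to ask about side effects, and daily home BP and algorithm-driven chemistry panels come on top. An excess of AEs in that arm could partly reflect detection. Under the illustrative model the inflation runs from none with full recall to 8.7-fold for events forgotten within 2 weeks under two-weekly contact. Transient symptoms are the most exposed. It does not follow that safety cannot be assessed relative to control, because the common assessments give equal scheduled opportunity. The plan should be amended, since the change is cheap and affects what the DSMB sees.

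**What to change.** 1. Reconcile the four statements into one rule. Every AE that meets a single stated definition is entered in the database in both arms, with seriousness and relatedness as recorded fields and not as conditions for entry. The definition must say whether trivial events count, and the log, the form and the annual report must all use it. Simply entering whatever is on the present log would keep its exclusions.
2. Add a source-of-detection field: common assessment, intervention-only call or home BP, algorithm-driven laboratory test, other.
3. In any by-arm AE summary for Aim 2, including those for the DSMB, base the comparison on AEs elicited at the common assessments. Tabulate those first found at intervention-only contacts separately, and show kidney and electrolyte findings with the number of tests per arm.
4. Have AE inquiry at the common visits done by existing staff other than the blinded BP assessor. Answers about drug effects at month 4 could reveal the arm before the month 8 and 12 readings, even if asked after that day's BP.

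The cost is a wording change, one added database field, somewhat more AE data entry, and a division of tasks at the common visits. No visits are added. For events already recorded, sites can enter the logged ones and code the source where the record shows it.
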